8.2 Participant Exclusion Criteria

Participants will be excluded from the study if they:

1. Are unwilling or unable to provide informed consent (determined during the Consent process and during Consent Quiz); and
2. Are currently in jail, prison or other overnight facility as required by court of law or have pending legal action that could prevent participation in study activities (determined by Prisoner Status Assessment at each study visit).

8.3 Strategies for Recruitment and Retention

Potentially eligible patients will be identified in the electronic health record and sent an invitational recruitment letter/secure message. Within approximately a week of mailing recruitment letters/sending a secure message, research staff will contact participants by phone to determine if they are interested and eligible, using the IRB-approved recruitment script, verbal consent and screening questions.

Study participants will be compensated \$75 for completing the Baseline appointments and baseline urine drug screen, and \$100 for completing the 12-week Follow-up appointment and follow up urine drug screen.

During the 12-week active phase of the study (the 12 weeks of EMA and sensor data collection via smartphone and smartwatch), research staff will contact participants to encourage them to continue their participation and/or troubleshoot any problems that may arise with their smartphone, smartwatch or EMA. Staff will also contact (e.g., call, text, email) participants if sensor data is not being recorded from the smartphone, smartwatch and/or if there is a lapse in responding to EMA prompts on the smartphone. If there are unexpected issues or problems with the technology (study equipment, study apps, social media download) that research staff cannot resolve with the participant, research staff may need to contact technical support personnel at Dartmouth using a 3-way or conference call to assist the participant with troubleshooting technical issues.

To be considered engaged in the study, an individual must respond to a minimum number of EMA prompts and have recorded a minimum number of smartphone/smartwatch sensor data on 7 out of the first 14 days of study participation. An individual will be contacted via phone, text, and/or e-mail by research staff after two days with no EMA or sensor data collected. If an individual does not meet the engagement criterion AND is non-responsive to research staff outreach in the first 14 days of study participation, then the individual will be considered a “non-engager” and the study team will continue to recruit until 50 (if recruitment is faster than anticipated, we will recruit up to 75) “engaged” individuals are enrolled. Non-engagers will not be withdrawn from the study, as we will attempt to collect all possible data from all participants.

To aid retention and adherence with the digital health data collection, participants will be compensated up to \$21 per week for completing EMAs, up to an additional \$10 per week bonus for completing a minimum of 80% of received EMAs, and up to \$14 per week for carrying their smartphone at least 8 hours per day and wearing the smartwatch at least 18 hours per day. At the end of the 12-week active phase of the study, participants will receive a \$50 bonus for either using their personal smartphone (to help offset the cost of their data plan) or returning a study-provided smartphone, and a \$50 bonus for returning the study-provided smartwatch. Finally, participants who consent to the social media portion of the project will receive up to an additional \$180. Total possible compensation will be up to \$820 over the course of the 12-week active study phase. In addition to the earnings and bonuses (described above), an individual who completes a minimum of 80% of received EMAs within a given week will qualify for a drawing at the end of that week where the individual could win a \$50 prize. Each individual will have an opportunity to participate in up to 12 drawings over the 12 weeks. During the 12-week active study phase, any incentives, bonuses, and/or drawings earned will be uploaded weekly to a reloadable debit card.

Total compensation will be up to \$995 for participating in all study activities.

9.0 SITE SELECTION

9.1 Number of Sites

We will recruit approximately 50 (if recruitment is faster than anticipated, we will recruit up to 75) participants from KPNC (part of the Health Systems Node) who have had treatment at KPNC's Addiction Medicine Recovery Services (AMRS) programs.

9.2 Site Characteristics

The AMRS programs at Kaiser Permanente Northern California (KPNC) offer a broad range of services (medical services onsite, group and individual therapy, family therapy). Staffing includes physicians, social workers, and substance use counselors. The AMRS programs offer MOUD treatment for buprenorphine.

We anticipate roughly 180 patients with OUD on buprenorphine for at least 2 weeks will be approached for recruitment. Assuming a conservative 30% recruitment rate, we anticipate approximately 50 (if recruitment is faster than anticipated, we will recruit up to 75) patients enrolled over the 6-month study recruitment period.

9.3 Rationale for Site Selection

KPNC was selected based on its ability to (1) provide access to individuals who are in MOUD buprenorphine treatment and (2) provide access to EHR data on treatment retention, medication adherence, and service utilization. KPNC serves a mixed population (in terms of severity) of individuals in treatment for OUD. KPNC is an integrated healthcare system that maintains a data repository, the Virtual Data Warehouse, which has combined EHR data (e.g., demographics, membership, diagnoses, service utilization, pharmacy, lab data) with several other data sources, including medical claims data (e.g., non-Kaiser pharmacy data). Participant EHR data will include urine toxicology results, buprenorphine dispensation data, and treatment utilization data (e.g., substance use, primary care, psychiatry, emergency department, inpatient, phone appointments, secure messages) which reflects any encounters with the health system.

10.0 STUDY PROCEDURES

10.1 Screening

Patients will be screened by phone/video to determine eligibility. After briefly explaining the study, conducting prisoner assessment and obtaining verbal consent, research staff will perform the screening and complete the Inclusion/Exclusion form. If eligible, research staff will schedule the initial baseline phone/video appointment and send consent documents to participant for their review before their appointment. (see Section 11).

The screening will take approximately 10 minutes to complete.

10.2 Consent and Baseline

10.2.1 Informed Consent Procedures for Participants

Informed consent will be obtained by phone/video and documented online using an electronic signature. Participants will have been given an opportunity to review consent documents prior to the baseline phone/video appointment (see 10.1). At the initial baseline phone/video appointment, research staff will review all elements of consent with participant over the phone/video (procedures, risks, benefits, compensation, etc.) and provide an opportunity for participant to ask questions.

Once questions are answered, the participant will be asked to pass a brief consent quiz to document comprehension of the study activities. Any incorrect responses will be reviewed with the participant by research staff. After providing an electronic signature, participants will be able to print a copy of the forms to keep for their records. The informed consent process and quiz will take approximately 30 minutes to complete. Patients will be provided two opportunities to pass the quiz, at which point they will be determined ineligible.

10.2.2 HIPAA Authorization and Medical Record Release Forms

The study site will obtain authorization from participants for use of protected health information, such as access to their EHR and medical claims data. The site will be responsible for communicating with their IRB(s) or Privacy Boards and obtaining the appropriate approvals or waivers to be in regulatory compliance.

10.2.3 Baseline

The baseline will be conducted in two or three phone/video appointments: the first appointment will consist of informed consent and the baseline assessment, and the second appointment will consist of urine drug screen, setting up study devices, installing study applications (“apps”), and learning to use devices and apps. If needed, appointments will be conducted with HIPAA compliant IRB-approved video capability.

Initial baseline appointment (1 hour): After conducting prisoner assessment and providing informed consent, participants will complete the Baseline assessment (see Section 11). The Baseline assessment consists of interviewer-administered measures examining participant characteristics, current substance use (e.g., tobacco, alcohol, opioids, and other drugs), substance use and mental health disorders, and the impact of COVID-19.

Once the first Baseline appointment is completed, participants will be mailed their urine drug screen (UDS) kit, their smartwatch and study smartphone (if applicable) and technology training documentation.

Second Baseline appointment (1 hour): Once the equipment is received, research staff will schedule a second phone/video appointment with participant to review the urine collection and technology training documentation. Research staff will walk through the set-up, use and care of smartphone and smartwatch, installation of the study app and the Garmin Connect app, as well as instructions for initiating and completing the daily EMAs. Research staff will also instruct participants to collect urine sample and upload results. If any technical issues arise, the research staff have the ability to upload the photographs into REDCap for the participant. Once the urine drug screen results are received, participants will be reimbursed \$75 (via gift card) for completion of the baseline.

A third baseline appointment can be arranged if needed. We don't anticipate this will occur frequently as the tasks should easily be completed within two baseline appointments.

Research staff will explain to participants that EMA data will not be monitored in real-time, and participants will be instructed to call their medical providers or 911 if they have an immediate crisis or an emergency.

Participants will be instructed on how to download social media (for those who consented to this part of the study). Social media data will be downloaded by the participant directly from the social media platform to a secure server at Dartmouth using a remote desktop at the beginning of the study.

Additional compensation will be provided for social media data download, as well as participation in the active phase of the study (completing EMAs, wearing the smartwatch and carrying the smartphone) (described in Section 8.3).

If there are unexpected issues or problems with the technology (study equipment, study apps, social media download) during the active phase of the study that research staff cannot resolve with the participant, research staff may need to contact technical support personnel at Dartmouth using a 3-way or conference call to assist the participant with troubleshooting technical issues.

10.3 Premature Withdrawal of Participants

All participants will be followed for the duration of the study unless they withdraw consent, die, or the investigator or sponsor decides to discontinue their enrollment for any reason. Reasons for the investigator or sponsor terminating a participant from the study may include, but are not limited to, the participant becoming a threat to self or others.

Participants may withdraw voluntarily from the study at any time.

10.4 Study Halting Rules

As this is not a clinical trial and no treatment involved, risk is expected to be very low. There will be no study halting rules.

10.5 Follow-Up

A follow-up assessment will be completed approximately 12 weeks post-EMA start by phone/video. Research staff will administer an interviewer-based assessment to measure current substance use, participant experience with the study devices, treatment utilization, reasons for drop out (if appropriate), employment, insurance coverage, medication use/dose (if applicable),

and overdose. Participants will be mailed a UDS kit and asked to collect sample and upload test results to REDCap. If any technical issues arise, the research staff have the ability to upload the photographs into REDCap for the participant. Once the UDS results are received, participants will receive \$100 for completing the follow up assessment. Additionally, EHR, medical claims, and social media (if consented) data will be extracted/downloaded after participants complete the 12-week active phase of the study. Additional compensation will be provided for social media data downloads (if consented) and returning study equipment at the end of the active study phase (described in Section 8.3).

10.6 Participant Reimbursement

Participants will be compensated for their participation in this study (incentives described in Section 8.3). Compensation will be in accordance with the IRB of record's policies and procedures, and subject to IRB approval. Total compensation will be up to \$995 for participating in all study activities (\$75 for baseline assessment, \$100 for follow up assessment and up to \$820 for engagement in digital data collection). Payments for research participation in excess of \$600.00 in one calendar year are reportable to the Internal Revenue Service (IRS). Participants may be required to pay taxes on this money, as required by law, and will be asked to provide home address and social security number to receive study payments in excess of \$600.

11.0 STUDY ASSESSMENTS

11.1 Table of Study Assessments

Construct	Subdomain	Assessment Name	Interview (I) Extraction (E) Download (D)	Time estimate (minutes)
	Verbal Consent	Verbal consent	I	5
Screening	Prisoner Status	Prisoner Status Assessment (Repeat Prisoner Status Follow-up at each study visit)	I	2
	Study eligibility	Inclusion/Exclusion Form	I	3
			Total Time	~10 minutes
Baseline	Prisoner Status	Prisoner Status Assessment	I	2
	Consent/Locator	E-Consent E-HIPAA Authorization Consent Quiz Locator Form (to be completed at each call)	I	30
	Demographics Substance Use	PhenX Core Tier 1, PhenX Core Tier 2, NSDUH (subset of measures/question: demographics & current substance use)	I	25
	COVID-19	Baseline Assessment	I	2
	DSM-5 diagnosis	NetSCID-5	I	20-45
	Recent use	Urine Drug Screen	I	10
			Total Time	~85-120 minutes

	Social Media	Social media images/texts of postings & comments, reactions, date/time	D- from social media platform via remote desktop	At the beginning of the study
	Prisoner Status	Prisoner Status Assessment	I	2
Follow-up	Substance Use	PhenX Core Tier 1 (subset of measures: current substance use)	I	20
	Participant Experience Employment Treatment utilization Insurance coverage	Follow-up Assessment		15
	Recent use	Urine Drug Screen	I	10
			Total Time	~60 minutes*
	Social Media	Social media images/texts of postings & comments, reactions, date/time	D- from social media platform via remote desktop	At the end of the study
	Health records	EHR	E**	Retroactively from 12 weeks post-EMA start to 12-months prior to EMA start
	Health records	Medical Claims	E**	Retroactively from 12 weeks post-EMA start to 12-months prior to EMA start

*Follow-up appointment will take approximately 45 minutes to complete assessments plus another ~15 minutes to instruct participants on how to return study equipment (for a total of approximately 60 minutes).

**Note: EHR/Medical Claims data will be extracted by the Data Analyst approximately 16-weeks after completion of study and includes data 12 months prior to EMA start through 12 weeks post-EMA start.

11.2 Active Study Phase Digital Health Assessments

Construct/ domain	Subdomain	Assessment name	Wearable (W) Carryable (C) Self-report (SR)	Occurrence
Smartwatch/ Smartphone/ Self-Report	Distance, physical activity, sleep	Ambulatory Physiological Assessment using Mobile Sensors	W	Wear at least 18 hours/day, data transmitted real-time for 12 weeks
	Phone activity, WiFi/Bluetooth logs, ambient light, proximity, location, audio/conversation	Passive Assessment using Mobile Sensors	C	Carry smartphone at least 8 hours/day, data transmitted real-time, for 12 weeks
	Ecological Factors	Ecological Momentary Assessment (EMA) (including self-report of drug use)	SR	Up to 3x/day for 12 weeks
	Self-Regulation	Momentary Self-Regulation Scale 12-item	SR	Up to 3x/day for 12 weeks

11.3 Description of Measures

11.3.1 Prisoner Status Assessment

Prisoner status must be assessed for each participant at each separate encounter (i.e., all study contacts [e.g., screening appointment, baseline appointments, and follow-up appointment], as this study will not apply for OHRP Prisoner Certification). Due to the high-risk nature of this population becoming involved in the criminal justice system, assessment is required.

11.3.2 Inclusion/Exclusion

This form will be used to obtain information on inclusion and exclusion criteria to document eligibility. Eligibility is assessed continually as appropriate. Only participants who continue to meet study eligibility criteria will be permitted to continue with study procedures.

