information, Wi-Fi & Bluetooth logs, sleep, ambient light, and proximity will be passively collected via smartphone. After the 12-week active study phase, participants complete a follow-up phone/video visit. At the follow-up phone/video visit, research staff will administer an interview-based assessment to measure current substance use (e.g., tobacco, alcohol, opioids, and other drugs), participant experience with the study devices (including wearing the smartwatch, carrying the smartphone, and responding to EMAs), treatment utilization, reasons for drop out (if appropriate), medication use/dose (if applicable), and overdose. For those who consent, social media data will be downloaded by the participant directly from the social media platform to a secure server using a remote desktop at the beginning of the study and at the end of the study. EHR and medical claims data (e.g., pharmacy claims data for Kaiser and non-Kaiser pharmacies if a claim was paid for) will be extracted 16 weeks after study completion (data will be collected 12 months prior to EMA start through 12 weeks after EMA start). Prior to each encounter (screening, baseline and follow-up), research staff will administer a brief prisoner status assessment to confirm study eligibility (non-prisoner status).

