7.2 Secondary Outcome Measure(s)

The secondary outcome measures will include:

1. OUD treatment retention (days retained in OUD treatment program) based on EHR data;
2. Days covered on MOUD based on EHR and EMA data; and
3. Non-prescribed opioid use (including illicit opioid use) based on EMA data.

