7.3 Other Outcome Measures

Other outcomes will include:

1. Frequency of missed buprenorphine doses based on EMA data;
2. Percentage of days with access to prescription medication exceeding a threshold (e.g., 80%) over the 12-week study period (a dichotomous variable based on pharmacy dispensation and medication orders from the EHR data extraction);
3. Number of days of non-prescribed opioid use (including illicit opioid use) in the last 4 weeks (weeks 9-12 post study consent) based on EMA data; and
4. Each non-prescribed opioid use event during the 12-week study period based on EMA data.
5. Each missed dose event during the 12-week study period based on EMA data.
6. Each missed visit to OUD treatment program during the 12-week study period based on EHR data.

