8.1 Participant Inclusion Criteria

Individuals participating in the study must:

1. Have been active in Kaiser outpatient buprenorphine treatment for OUD for the past 2 weeks (determined at screening);
2. Be ≥ 18 years old (determined at screening);
3. Be able to understand English (determined at screening);
4. Be available to participate in the full duration of the study (12 weeks) (determined at screening);
5. Have an active email account and willing to provide the email address to researchers (determined at screening);
6. Permit researchers to access personal electronic health record (EHR) and medical claims data (determined at screening);
7. Be willing to carry and use personal or study provided smartphone for 12 weeks (determined at screening); and
8. Be willing to wear a smartwatch continuously (except during pre-defined activities such as showering) for 12 weeks (determined at screening).

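### Does Section 11.3.2 end data collection when a participant leaves buprenorphine treatment?

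*Combined protocol and SAP*

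**What the plan says.** Section 11.3.2 describes the Inclusion/Exclusion form. It says that eligibility is checked on a continuing basis where appropriate, and then: "Only participants who continue to meet study eligibility criteria will be permitted to continue with study procedures". It does not say which criteria are meant.

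Other sections bear on the question:

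- **Section 8.1**, criterion 1: "Have been active in Kaiser outpatient buprenorphine treatment for OUD for the past 2 weeks (determined at screening"). The other seven inclusion criteria carry the same timing label.
- **Section 8.2**, exclusion 2 (custody or pending legal action): "determined by Prisoner Status Assessment at each study visit".
- **Section 2.4**, before each encounter: "research staff will administer a brief prisoner status assessment to confirm study eligibility (non-prisoner status").
- **Section 8.3**: "Non-engagers will not be withdrawn from the study, as we will attempt to collect all possible data from all participants".
- **Section 10.3**: "All participants will be followed for the duration of the study unless they withdraw consent, die", or the investigator or sponsor discontinues them, for which any reason is enough.

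The outcomes that depend on continued EMA include secondary outcome 3 in Section 7.2, "Non-prescribed opioid use (including illicit opioid use) based on EMA data", and item 3 of Section 7.3, days of non-prescribed opioid use "in the last 4 weeks (weeks 9-12 post study consent) based on EMA data". Days covered on MOUD (Section 7.2, item 2) and missed doses (Section 7.3) also use EMA.

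**The concern.** The sentence in Section 11.3.2 is mandatory and has no stated limit. If it reached criterion 1, a participant who left buprenorphine treatment would have to stop all study procedures, including EMA and sensing. Sections 8.3 and 10.3 lean the other way, towards keeping people in and collecting what can be collected.

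The stakes would be real. EMA would stop at an event closely related to what it measures. Opioid use, missed doses and EMA-based days covered would be censored informatively, and anyone stopped early would have nothing for the weeks 9-12 outcome. The EMA response rate, a primary feasibility measure, could move up or down depending on whether undelivered prompts count in its denominator. Retention from EHR data would be largely unaffected because it is extracted retrospectively. Wear days counted over the full 12 weeks would not be inflated.

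**Working it through.** The plan states no figure on this point, so there is none to reproduce. The main check compares the sections; the arithmetic only scales the broad reading.

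**1. Does criterion 1 lapse when someone leaves treatment?** It asks for activity in treatment over the two weeks before screening. Section 2.3 likewise ties treatment status to the time of consent and the two weeks before enrolment. A participant who leaves treatment in week 6 still met that criterion on the date it was assessed. To make the person ineligible, the criterion would have to require continuing treatment, and no section says that.

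**2. What is re-checked?**

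| Item | When assessed | Where |
|---|---|---|
| Inclusion criteria 1-8 | Screening | 8.1 |
| Inclusion/Exclusion Form | Screening only | 11.1 |
| Consent (exclusion 1) | Consent process and quiz | 8.2, 10.2.1 |
| Prisoner or legal status (exclusion 2) | Every visit | 2.4, 8.2, 11.1, 11.3.1 |

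Section 2.4 calls the repeated prisoner check a confirmation of eligibility, and Section 15.9 requires suspension of research contact on incarceration. There are also eligibility steps before the active phase: phone screening is only preliminary (Section 2.4), failing the consent quiz twice makes a person ineligible (Section 10.2.1), and screening and baseline assessments are reviewed before enrolment (Appendix B, Participant Protection). The sentence in Section 11.3.2 therefore has work to do without touching treatment status.

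**3. Would any procedure trigger a stop?**

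- EHR and claims data are extracted about 16 weeks after study completion (Sections 2.4, 6.1 and 6.2).
- EMA data are not monitored in real time (Section 10.2.3).
- Staff contact in the active phase is for encouragement, technical problems or lapses in data (Section 8.3).
- The only visit after baseline is about 12 weeks after EMA start (Section 10.5), when EMA is ending.

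No step directs staff to establish whether a participant is still in treatment.

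**4. Scale if the broad reading were applied.** The time of leaving is an assumption.

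- Maximum prompts per participant: 12 × 7 × 3 = 252.
- Prompts lost on leaving at the end of week w: (12 − w) × 7 × 3.

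| w | Prompts lost | Share of 252 |
|---|---|---|
| 2 | 210 | 83% |
| 4 | 168 | 67% |
| 6 | 126 | 50% |
| 8 | 84 | 33% |
| 10 | 42 | 17% |

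Counting weeks from EMA start for simplicity, anyone leaving by the end of week 8 gives 0 of 28 days to the weeks 9-12 outcome. If 10% to 30% left treatment (assumed), that would be at most 50 × 0.10 = 5 to 50 × 0.30 = 15 people.

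A bias in the opioid-use rate needs further assumptions. Suppose use on 8% of days in treatment, a share L leaving at day 42 of 84, and use on p% of days afterwards. The 84-day rate is (1 − L) × 8 + L × (0.5 × 8 + 0.5 × p).

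- p = 8: 8.0%, no bias.
- L = 0.10, p = 20: 7.2 + 0.10 × 14 = 8.6%.
- L = 0.30, p = 40: 5.6 + 0.30 × 24 = 12.8%.

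Against a censored 8.0%, the understatement runs from 0 to 4.8 points. None of these inputs comes from the documents. The formula also treats every day after leaving as observed. If response fell after leaving treatment, continued prompting would not recover all the missing use days, so these figures cannot be taken as an effect of the wording.

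**The case for a change.** The best case for a change is that Section 11.3.2 is operative text. Section 15.15 treats any departure from the protocol as a deviation and mentions inclusion and exclusion criteria when describing major ones. Appendix B makes those criteria a particular concern for monitors. Staff could learn of a departure from treatment during a troubleshooting call, and a cautious coordinator or monitor could read the sentence broadly. Criteria 7 and 8 raise the same issue: they ask for willingness to carry the phone and wear the watch, while Appendix B lets participants put the devices aside. One sentence would remove the doubt at almost no cost.

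It stands that the section does not name its criteria and that staff might learn of a departure by chance. The conflict with other sections is weaker than it looks:

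- Section 8.1 resolves the ambiguity through its timing labels rather than contradicting Section 11.3.2.
- Section 10.3 permits discontinuation for any reason, so the clash would be between an automatic and a discretionary stop.
- The operative sentence in Section 8.3 concerns non-engagers; only its stated reason extends to everyone.
- Criteria 7 and 8 are about willingness, again judged at screening.

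The follow-up interview's question about reasons for drop-out does not settle the matter, since it does not say whether treatment or study drop-out is meant. Whether the EMA response rate in Section 7.1 uses delivered or scheduled prompts is a separate gap in definition, present however Section 11.3.2 is read.

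**Conclusion.** No change to the plan follows. Section 11.3.2 is loosely worded, but Sections 2.3, 2.4, 8.1, 8.2, 11.1 and 11.3.1 together give it a coherent meaning: after enrolment, the eligibility criterion re-assessed at visits is prisoner or legal status. Leaving buprenorphine treatment does not undo a criterion met at screening, and no planned procedure looks for it during the active phase. On that reading the loss of EMA data is zero. A clarifying sentence would only record what the plan already implies.

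The losses shown for the broad reading rest on assumed leaving times and rates and are not evidence of bias. The conclusion assumes that staff follow the timing labels in Sections 8.1 and 8.2. It would weaken if site instructions outside these documents told staff to stop data collection when treatment ends. The setting also limits the stakes: Section 2.0 describes an observational pilot that is not powered for specific hypotheses, and the EHR-based retention outcome is largely protected by retrospective extraction.
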